## **4.0 OUTCOME MEASURES**

### **4.1 Primary Outcome Measure**

The primary outcomes in this study are (1) OUD and other SUD treatment linkage/retention, (2) opioid abstinence, (3) adherence to MAT, and (4) linkage/retention in psychosocial services.

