## 8.0 STUDY ASSESSMENTS

*A full and complete list of all assessments used in the study is to be included in the following sections.*

Outcome	Domain	Name	Source	Screen	Base	PreNat	2mo	6mo
1/2ary	Engage	Treatment Services Review	Self-Report		x	x	x	x
1/2ary	SUD	Timeline Follow Back	Self-Report		x	x	x	x
1ary	Engage	Substance use treatment visits	Medical record		x	x	x	x
1ary	Engage	Psychiatric care visits	Medical record		x	x	x	x
1ary	SUD	Urine toxicology	NA	x	x	x	x	x
1ary	Engage	Social service visits	Agency record		x	x	x	x
2ary	HIV/HCV risk	Risk Behavior Assessment	Self-Report		x	x	x	x
2ary	Social	Maternal Social Support Index	Self-Report		x	x	x	x
2ary	Social	Parenting Stress Index-Short Form	Self-Report		x	x	x	x
2ary	Social	Maternal Attachment Inventory	Self-Report		x	x	x	x
2ary	Engage	Adequacy of Prenatal Care Utilization	Medical record				x	
2ary	Engage	Pre/post maternal care visits	Medical record		x	x	x	x
2ary	Engage	Pediatric visits	Medical record		x	x	x	x
2ary	SUD	Neonatal abstinence syndrome	Medical record				x	
2ary	Engage	Pre/post maternal care visits	Medical record		x	x	x	x
2ary	Engage	Pediatric visits	Medical record				x	x
Covar	SUD	Drug Abuse Severity Test 10	Self-Report		x	x	x	x
Covar	SUD	Alcohol Use Disorder	Self-Report		x	x	x	x

		Identification Test						
Covar	SUD	Fagerstrom Test for Nicotine Dependence	Self-Report		x	x	x	x
Covar	Health	Short Form 36	Self-Report		x	x	x	x
Covar	Psych	Patient Health Questionnaire	Self-Report		x	x	x	x
Covar	Social	Addiction Severity Index (employment)	Self-Report		x	x	x	x
Covar	SUD	DSM 5 Checklist	Self-Report	x	x	x	x	x

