### **10.3 Statistical Methods for Primary and Secondary Outcomes**

We will employ descriptive statistics to calculate measures of central tendency, frequencies, and proportions for patient demographics and substance use, health, social, and mother/child indicators. T-tests and  $\chi^2$  tests will be used to assess mean and proportion differences between outcome variables by study group at each time point. Specifically, we will examine unadjusted differences between PN and standard care patients for linkage/retention in: (a) OUD and other SUD counseling, (b) psychosocial services, and (c) pre/postnatal care compared to standard care. We will also examine unadjusted differences between groups for MAT adherence, opioid and non-opioid drug abstinence, HIV/HCV risk behaviors, depression/anxiety, and child/mother outcomes (e.g., NAS, parental stress, attachment, and maternal social support).

We will also develop a series of multilevel models to examine treatment, time, and covariate effects associated with our primary and secondary study outcomes (Equation 1). The multilevel framework allows for a flexible treatment of time where change as a putative outcome may be nonlinear, accelerates, or decelerates at different rates across time. The framework is also forgiving of unequal numbers of observations and unequal spacing of observations across participants (i.e., missing data patterns). Models will be constructed using a model-building sequence proposed by Singer and Willett, in which: (a) empirical growth plots will be examined visually, (b) an unconditional model will be fit, (c) an unconditional linear growth model will be fit, (d) unconditional non-linear models (e.g., a piecewise model) will be fit, (e) the models' fit in the prior steps will be compared using the Akaike Information Criterion to determine the best growth model, and (f) time-invariant (e.g., baseline mental health diagnoses) and time-varying (e.g., drug use) predictors will be added to the models. We will examine the association of these predictors with the study outcomes across time. We will also test higher levels of service linkage/retention as moderators for improvements in (a) abstinence, (b) HIV/HCV risk behaviors, (c) depression/anxiety, and (d) child/mother outcomes.

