Included below is the equation for a random-coefficient multilevel growth model. The  $Y$  in the equation represents a binary opioid abstinence outcome, for example, for the  $i$ th participants at time  $t$ . The symbol “~” indicates that the binary response with linear predictor given by the right hand side in the context of a logistic mixed effects model, with random effects for site, and potentially time within site. The primary variable types are represented in the equation: (a) *time* is

a variable representing time that may require multiple time variables in the event of nonlinear change (e.g. quadratic), (b) *time-varying* is any variable measured at each time point, and (c) *invariant* is a variable measured at the person-level. The model below can easily be extended to a third level if it is determined that there is variability in coefficients across centers.

	Level 1: $Y_{ti} \sim \beta_{0i} + \beta_{1i}time_{ti} + \beta_{2i}time\text{-}varying_{ti} + \beta_{3i}time_{ti}time\text{-}varying_{ti}$
Equation 1.	Level 2: $\beta_{0i} = \gamma_{00} + \gamma_{01}invariant_i + u_{0i}$
	$\beta_{1i} = \gamma_{10} + \gamma_{11}invariant_i + u_{1i}$

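### Section 10.3 adds time-varying drug use to the models meant to show the navigation effect, names no site-aware model free of post-randomisation covariates, and tests a primary outcome (linkage/retention) as a moderator

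*Combined protocol and SAP*

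**What the plan says.** Section 10.3 describes two layers of analysis.

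- **Unadjusted tests.** T-tests and chi-square tests "will be used to assess mean and proportion differences between outcome variables by study group at each time point". They have no site term.
- **Multilevel models.** A series of models will "examine treatment, time, and covariate effects associated with our primary and secondary study outcomes". Steps (a) to (e) are growth plots, unconditional models and a comparison by Akaike criterion. Predictors enter only at step (f): "time-invariant (e.g., baseline mental health diagnoses) and time-varying (e.g., drug use) predictors will be added to the models". The next sentence gives the use of these predictors as examining their association with the outcomes over time.

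Equation 1 contains a time-varying term and its product with time. A time-varying predictor "is any variable measured at each time point". The example outcome "represents a binary opioid abstinence outcome", fitted "in the context of a logistic mixed effects model, with random effects for site". As printed, the equation has participant-level random effects only. Arm is not written as its own term, and a centre level is optional.

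The primary outcomes in section 4.1 are "1) OUD and other SUD treatment linkage/retention, (2) opioid abstinence, (3) adherence to MAT, and (4) linkage/retention in psychosocial services". In section 10.1.1, H1 expects PN to improve linkage and retention, H2 expects more PN women to be drug abstinent, and H3 makes engagement/retention a moderator of improvement in abstinence and other outcomes. Section 10.3 repeats that moderator test.

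Section 10.1 stratifies randomisation by hospital site in blocks of 6. Section 10.2.2 promises odds ratios by arm that account for clustering within site. It also says that definitive estimation and testing are not the pilot's aim.

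**The concern.** Randomisation protects a comparison of arms only if nothing that treatment can change is held fixed. Drug use at follow-up is such a variable, by the plan's own H2. Holding it fixed removes whatever part of the PN effect runs through it. It can also bring in bias from unmeasured causes shared by drug use and the outcome. Where the outcome is opioid or drug abstinence, the predictor may overlap the outcome itself.

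H3 has a related problem. Women are grouped by an engagement status reached after randomisation and expected to differ by arm, so the comparison is not between randomised groups. Section 10.3 also leaves open whether the thing moderated is the arm effect or the change over time.

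Aim 3 (section 2.1, Table 1) is to show preliminary benefit of PN, as a foundation for a fully powered trial. An odds ratio at a fixed level of drug use answers a different question from the effect of offering PN.

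**Working it through.** **1. Timing and role of the two variables.**
- *Drug use.* Randomisation follows the baseline assessment (section 7.4). The section 8.0 table schedules "Timeline Follow Back" and urine toxicology at baseline, end of the prenatal phase, 2 months and 6 months, so three of the four assessments come after randomisation. The table marks the first instrument 1/2ary and the second 1ary.
- *Linkage/retention.* It supplies primary outcomes 1 and 4, is the target of H1, and is the H3 moderator.

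**2. The plan's own figures reproduce and do not bear on the point.** Recruitment: (141 + 58) × 15/12 × 0.70 × 0.70 = 121.9, so 122. Confidence-limit factor with 61 per arm, odds ratio 1 and full follow-up: exp(1.96 × √[2/(61p(1−p))]). This gives 2.03 at p = 50% and 2.98 at p = 12%, in line with the stated 2 to 3.

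**3. One-visit illustration, all inputs assumed.** Drug use is 50% under standard care and 33.3% under PN. Retention is 50% in non-users and 20% in users, in both arms.
- Standard care: 0.5 × 0.20 + 0.5 × 0.50 = 0.35.
- PN: 0.333 × 0.20 + 0.667 × 0.50 = 0.40.
- Total odds ratio: (0.40/0.60)/(0.35/0.65) = 1.24. Given drug use, it is 1.00.

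**4. Wider ranges, simulated with assumed effects and a site term.** PN lowers the odds of drug use by a factor of 0.67 to 0.33, and drug use lowers the odds of the outcome by 0.50 to 0.125.
- No direct PN effect: total odds ratio 1.07 to 1.63, and about 1.00 with drug use added.
- Direct odds ratio 1.5: total 1.57 to 2.30, and about 1.5 with drug use added (49% to 87% of the log odds ratio kept).
- Unmeasured cause shared by drug use and outcome, no direct effect: the adjusted value falls to 0.84 to 0.95 although the total effect is beneficial.

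A second calculation used a mixed model of Equation 1's form, without a site term, over 90 assumed combinations. The conditional odds ratio was below the total in 78 and above it in 12. All 12 had a direct PN effect and a drug-use change of 7 points or less. These counts are a property of the grid chosen.

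**5. Overlap when the outcome is opioid abstinence.** Suppose the predictor is any drug use, opioids included, at the same visit. Let p be opioid use and q the share of opioid-abstinent women using other drugs. Among users, the odds of opioid abstinence are (1−p)q/p. With p = 40% (standard care) and 25% (PN), the total odds ratio is (0.75/0.25)/(0.60/0.40) = 2.00. The conditional value is 2.00 × q(PN)/q(standard care). With 45% under standard care, it is 2.00, 1.33 or 1.00 for q(PN) of 45%, 30% or 22.5%.

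**6. Site.** Assume two equal sites, a site difference of 1.0 on the logit scale and a within-site odds ratio of 2.00. Standard-care rates of 26.9% and 50.0% average 38.5%; PN rates of 42.4% and 66.7% average 54.5%. Ignoring site gives (0.545/0.455)/(0.385/0.615) = 1.92, a small loss. With two sites, a between-site variance rests on 1 degree of freedom. The 95% limits for the site SD are √(1/χ²) at the 97.5% and 2.5% points, about 0.45 and 32 times the estimate.

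**7. H3.** Suppose neither PN nor engagement affects abstinence and a shared factor drives both engagement and abstinence (assumed).
- Engagement still shows an odds ratio of 1.24 to 3.40 with abstinence.
- The arm-by-engagement odds ratio stays near 1 (0.98 to 1.04) if the factor drives engagement equally in both arms. It is 0.49 to 0.89 if the link is weaker under PN and 1.12 to 2.03 if stronger.
- The engagement-by-time odds ratio is 0.96 to 1.00 if the factor weighs equally on baseline and follow-up abstinence. It is 1.35 to 1.50 if it weighs 0.5 and 1.0 per SD, for engagement loadings of 1.0 to 1.5.

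**The case against.** The defence has real substance. Drug use is an example, not tied to any outcome. The sentence after step (f) gives the use of the added predictors as association, and nowhere is the PN estimate said to come from a model containing drug use. Arm can fill the person-level slot of Equation 1. The section 8.0 table marks seven instruments as covariates, including a drug abuse severity test, and the team may have meant one of these. The visit-wise tests are valid, and stratification in blocks of 6 keeps them close to site-balanced. The trial is a pilot.

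All of this stands, and it rules out several stronger readings that a reader might infer:
- *That the plan commits to a drug-use-adjusted PN estimate, or has no valid arm comparison.* It does neither.
- *That site is ignored.* The model text names random effects for site, and the numerical cost of omitting it is small in the check above.
- *That drug use has no finite coefficient when the outcome is opioid abstinence.* That needs predictor and outcome to share definition, source and time window, which the plan does not state. With both self-report and urine collected, disagreement between them would remove the separation.

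The defence does not remove the gap. The covariate instruments are also repeated after randomisation. The models are said to examine treatment effects, and no model without post-randomisation covariates is named for them.

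**Conclusion.** The point holds as a low-to-moderate issue. A PN effect read from a model built through step (f) with drug use included would not be the effect of offering PN, and the plan names no alternative that also accounts for site. H3 is not a comparison of randomised groups.

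The size cannot be obtained from the documents, which give no effect sizes. Every odds ratio above rests on assumed inputs and shows direction and possible range only. Two further readings go too far. The shift is not always toward the null, since the conditional value can exceed the total when PN has a direct effect and changes drug use little. Nor is an H3 interaction necessarily spurious: it needs an arm-specific or time-specific link, and the mention in section 2.1 of outreach to women who disengage makes an arm-specific link possible without establishing it.

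The pilot disclaimer in section 10.2.2 lowers the weight of the point. Aim 3 and the planned larger trial keep it worth fixing.

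**What to change.** Change section 10.3 as follows.

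1. **Name the PN-effect model.** For repeatedly measured outcomes: arm, visit, arm-by-visit, site as a fixed effect (there are only two), the baseline value of the outcome where one exists, and at most a few baseline covariates named in advance. With three follow-up visits this is 1 + 1 + 2 + 2 + 1 + 1 = 8 coefficients, counting the intercept, before any further covariates. For outcomes assessed once, such as neonatal abstinence syndrome and Adequacy of Prenatal Care Utilization (2 months only in the section 8.0 table), use arm and site without visit or baseline-outcome terms.
2. **Name the contrast.** The team should state in advance which visit contrast is the PN estimate, and keep the unadjusted tests as support.
3. **Separate the time-varying models.** Put no post-randomisation covariate in the PN-effect model. Report models with time-varying predictors as exploratory associations, take no PN effect from them, and leave drug use out when the outcome is opioid or drug abstinence.
4. **Relabel H3** as an exploratory association or mediation analysis: engagement at an earlier visit predicting a later outcome, adjusted for baseline confounders. Keep the term moderator for baseline variables.

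The cost is wording only: no new data, and the sample size stays at 122. The downsides are that H3 is no longer a moderation test, and that the model and contrast must be chosen before the data are seen.

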#### 7.5 Treatment/Intervention

**Standard care.** The standard care condition at Magee and the University of Utah hospitals includes brief case management and referral. The brief case management involves the participant speaking to a hospital social worker who conducts a patient needs assessment in the areas of behavioral health and social services. All patients will be referred to MAT and any identified behavioral health or social service needs. For MAT, Magee-Womens Hospital offers resources for onsite induction to methadone or buprenorphine (mono-product), with continued methadone maintenance only provided by community partners and continued buprenorphine offered by an internal Magee clinic or community partners. University of Utah patients are offered buprenorphine induction and maintenance (buprenorphine-naloxone product) at a local University of Utah outpatient clinic or from community partners. Methadone services for University of Utah patients are only provided by community partners. Staff social workers at Magee and the University of Utah will be provided with information on the study each quarter during the study recruitment phase and be instructed to closely follow and not deviate from their hospital standard care protocol. These quarterly meetings/trainings will be delivered in order to prevent threats to internal validity and biasing study outcomes.

**Patient navigation (PN).** Details of the navigation can be found in the PN Intervention Manual. The PN intervention will be delivered by the study navigator. Table 4 contains details of the PN intervention. The PN intervention will initiate following participant recruitment. *It is important to note that in Table 2, PN sessions do not strictly coincide with specific weeks of pregnancy since the women can be recruited up to ≤32 weeks of gestation.* The prenatal portion of the intervention includes up to 10 sessions delivered prior to delivery. The postnatal portion of the intervention will be delivered as 4 sessions over 8 weeks. Women who complete the intervention before delivery will receive regular calls/texts until delivery wherein the navigator will encourage and reinforce abstinence and treatment retention (see SOP for continued engagement). All contact will be reported by staff in a participant contact log developed for the study that will be used to quantify level of patient contact.

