The primary goal of the current PN intervention is linking patients before and after delivery to treatment/psychosocial care and clinical support for participants' retention in those services. All PN patients will be referred to MAT by the study navigator (see standard care description above for site differences for MAT resources). *It is through the navigator linking and helping to retain participants to OUD, other SUD, medical, mental health, social, and family services that will stimulate positive short- and long-term outcomes for mother and infant.* While Magee and the University of Utah hospitals facilitate initiation into MAT, a major challenge for women is linking to services for ongoing MAT and subsequently being retained in care. Patients will be encouraged to work with their providers to choose the form of medication, buprenorphine or methadone, which will best meet their needs. The navigator will support and encourage the patient to follow through with this treatment. The PN intervention will also target better compliance with pre/postnatal maternal healthcare, more effective transition of newborns into pediatric care, and relapse prevention (i.e., Aim 2). The PN intervention specifically encompasses two complementary and necessary services: strengths-based case management (SBCM) and 1-to-1 clinical support (see Table 2). PN sessions will last 1-1.5 hours. Furthermore, given the challenges keeping this population engaged in care, the intervention emphasizes community outreach. For example, the navigator can visit the neighborhoods to meet participants' social and family networks to empathically encourage and support engagement with health, social services systems, and recovery support (i.e., narcotics anonymous, alcoholics anonymous) if patients become disengaged in care or follow up.

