## 10.0 STATISTICAL DESIGN AND ANALYSES

### 10.1 General Design

This study design for this project is a small scale, multisite, phase 2, single blinded, randomized clinical trial. Randomization will be stratified by hospital site and performed in blocks of 6 to ensure an even distribution of Magee and University of Utah participants in PN and standard care groups.

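### Randomization is stratified by site, but the each-visit tests ignore site and baseline, section 10.3 conflicts with itself on how site is modelled, and the role of the baseline outcome is not stated

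*Combined protocol and SAP*

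**What the plan says.** **Design.** Section 10.1: "Randomization will be stratified by hospital site and performed in blocks of 6". Section 6.1 gives two sites. Section 7.5 describes different treatment resources at each. At Magee, induction is on site, "with continued methadone maintenance only provided by community partners and continued buprenorphine offered by an internal Magee clinic or community partners"; in Utah, "University of Utah patients are offered buprenorphine induction and maintenance (buprenorphine-naloxone product) at a local University of Utah outpatient clinic" or from community partners. The navigation arm meets the same differences ("see standard care description above for site differences for MAT resources").

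**Each-visit tests.** Section 10.3 plans t and chi-square comparisons: "tests will be used to assess mean and proportion differences between outcome variables by study group at each time point". It then says "we will examine unadjusted differences between PN and standard care patients for linkage/retention" and applies the same unadjusted approach to the other outcomes.

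**Multilevel models.** Section 10.3 describes three things about site:

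- The text calls the model a "logistic mixed effects model, with random effects for site, and potentially time within site".
- Equation 1 has participant-level effects only (u0i and u1i) and no site index.
- The closing sentence offers a third level should coefficients turn out to vary by centre.

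**Baseline.** On predictors, section 10.3 says "time-invariant (e.g., baseline mental health diagnoses) and time-varying (e.g., drug use) predictors will be added to the models". It does not say how the baseline value of an outcome is used.

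**Precision.** Section 10.2.2 disclaims definitive testing. It still expects the trial to pick up strong signals of benefit, and it describes 95% intervals for odds ratios (OR) with clustering by site taken into account.

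**The concern.** Site was important enough to stratify on, and section 7.5 gives reasons why outcomes might differ by site. An analysis that leaves site out gives up some of what the stratification bought, and the each-visit tests do that by design. Only the multilevel models can deliver the site-adjusted intervals of section 10.2.2, and there the text and the equation describe different models. An analyst would have to choose between them, possibly after seeing the data, because the third-level trigger has no criterion.

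The baseline question is similar. Treatment arm fits the person-level (*invariant*) slot of Equation 1, so treatment and treatment-by-time effects are available. But γ01 then lets the arms differ at baseline. Including the baseline visit as a response row therefore does not by itself adjust the arm difference at follow-up.

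At stake are some power, the width of intervals for continuous outcomes, and a clear definition of the adjusted estimate that would inform the later fully powered trial.

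**Working it through.** The documents give no outcome rates, effects or correlations. Those below are assumptions, except in step 1.

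**1. The plan's own figures (section 10.2.2).** N = (15/12) × (141 + 58) × 0.70 × 0.70 = 121.9, which reproduces 122. With 61 per arm, the OR interval factor is exp{1.96 √[1/(61 p0 q0) + 1/(61 p1 q1)]}. With no effect and p = 0.5 this is exp(1.96 × 0.362) = 2.03. It is 2.17 at 0.3, 2.43 at 0.2 and 2.98 at 0.12. The stated 2 to 3 holds for common rates of about 0.12 to 0.88.

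**2. The site statements side by side.** Participant effects plus an optional third level fit together as a base model and an extension. The unconditional random site effect in the text conflicts with that pair.

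**3. A variance from two sites.** It rests on 1 df. The 95% interval for the site SD runs from 1/√5.024 = 0.45 to 1/√0.000982 = 31.9 times the estimate. The chance that the site variance is estimated as zero is P(F(1,120) < 1/[1 + 61 ICC/(1 − ICC)]). That is 68%, 57%, 37% and 28% for an intraclass correlation (ICC) of 0, 0.01, 0.05 and 0.10. The third-level trigger would thus turn largely on chance.

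**4. Leaving site out, binary outcome, one visit.** Simulation: 61 women per site, blocks of 6 within site, no dropout, 20,000 trials per cell, Pearson chi-square against logistic regression with fixed site. Monte Carlo SE is 0.2 points for type I error and 0.35 for power.

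| Site rates | Type I, unadjusted / site-adjusted | Power at OR 2.5, unadjusted / site-adjusted | Gain |
|---|---|---|---|
| 50/50 | 5.9% / 5.9% | 69.0% / 69.0% | 0 |
| 40/60 | 5.2% / 5.3% | 66.9% / 67.6% | 1 |
| 30/70 | 4.1% / 5.3% | 56.6% / 61.4% | 5 |
| 40/80 | 3.4% / 4.9% | 51.4% / 57.4% | 6 |

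A site-stratified Mantel-Haenszel test gives nearly the same power. The last two rows are near the top of the range; I take about 2 to 6 points as the fair statement for them.

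The unadjusted OR is pulled toward 1. At 30/70 with a within-site OR of 2, the treated rates are 0.462 and 0.824, average 0.6425. The control average is 0.50, so the unadjusted OR is 0.6425/0.3575 = 1.80. At 40/60 it is 1.95.

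The site-adjusted interval is wider. With no effect, SE = 1/√(Σ n_s p_s q_s / 4). At 40/60 this is 1/√(122 × 0.24/4) = 0.370, factor 2.06. At 30/70 it is 1/√(122 × 0.21/4) = 0.395, factor 2.17. The unadjusted factor is 2.03 in both.

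**5. Binary baseline outcome.** Gain in power at OR 2.5 from site plus baseline, by assumed outcome rates according to baseline status:

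| Baseline prevalence | 40/60 | 30/70 | 40/80 | 20/80 |
|---|---|---|---|---|
| 50% | 1 | 5 | 6 | 12 |
| 20% | −1 | 2 | 2 | 8 |
| 10% | −1 | 0 | 0 | 5 |

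Low prevalence is plausible because section 5.2 excludes women on MAT for more than 6 weeks.

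**6. Continuous outcome.** The t-test SE is √(2/61) = 0.1811 SD units. Baseline adjustment multiplies it by √(1 − r²), giving 0.1727, 0.1568 and 0.1449 for r = 0.3, 0.5 and 0.6. The t-test interval is therefore 5%, 15% and 25% wider.

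For a linear growth model (four equally spaced visits, compound symmetry), the SE of the final-visit difference with γ01 free is 0.1609, 0.1669 and 0.1699. With a common baseline mean it is 0.1576, 0.1473 and 0.1370. Leaving γ01 free costs 2%, 13% and 24% in width.

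**7. Repeated binary visits.** Logistic mixed model, random participant intercept only, three follow-up visits, site rates 30/70, participant SD 1.0 / 1.5, 600 trials per cell (Monte Carlo SE about 2 points). Power at 6 months:

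- no site, no baseline: 59% / 60%
- site only: 68% / 68%
- site plus baseline covariate: 69% / 71%

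**The case against.** The strongest reply is that this is a pilot with no power basis, that section 10.3 already plans covariate-adjusted multilevel models, and that no section makes the unadjusted tests the main analysis. All of that is true. It does not settle the matter, because those models are where site's role is left open and no baseline adjustment is named.

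Several objections to the size also stand:

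- The 5- and 6-point site gains need a 40-point gap between hospitals. Section 7.5 shows different resources, not different outcome rates.
- Binary baseline adjustment does little at low prevalence.
- A random site intercept barely differs from a fixed one in the treatment SE (ratio 0.990 to 0.998). The case for a fixed effect is clarity and the single degree of freedom.
- Adjusting changes the OR from marginal to site-conditional and widens its interval.

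A reader might go further than the documents allow in four ways.

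- *Site has three incompatible roles.* Only one of the three statements conflicts with the other two.
- *The planned model would be singular.* A correlated site intercept and slope was singular in 450 of 450 fits with two sites, but those fits had no participant effect. Section 10.3 mentions time within site only as a possibility and states no correlation.
- *Repeated-visit power would rise by about 10 points.* That gain is against a model with neither site nor baseline. Step 7 shows most of it comes from including site at all, which the text already intends.
- *The ways of using baseline are interchangeable.* With an effect growing linearly from baseline, 30/70 and SD 1.0, a four-row growth model with site and γ01 free gave 76% power. The covariate form using follow-up visits only gave 70%.

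**Conclusion.** The point holds and its effect is modest. Section 10.3 should be changed because it does not fix one model for site, and the each-visit tests leave out both the stratification factor and a baseline measurement already collected.

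No stated figure is wrong: the sample size and the interval factor both reproduce. A reader might infer inflated false positives. The opposite holds: the unadjusted tests become conservative and the unadjusted OR moves toward 1 as site rates diverge.

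The site gain is about 0 to 1 point of power at 40/60 and about 2 to 6 points at 30/70 or 40/80. The clearest benefit is for continuous outcomes, where the t-test interval is about 5% to 25% wider than the baseline-adjusted one. These sizes rest on assumed site rates, a within-site OR of 2.5, baseline correlations of 0.3 to 0.6, an even split by site and no dropout. The conflict in the text and the unstated baseline rule rest on no assumption.

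**What to change.** In section 10.3:

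1. Replace the random effects for site and for time within site with a fixed site effect. Delete the third-level sentence. Keep the participant random effects.
2. For outcomes measured at baseline, in a repeated-visit model include the baseline visit as a response row with one baseline mean common to both arms. In a single-visit regression, use the baseline value as a covariate.
3. For outcomes without a baseline value, such as neonatal abstinence syndrome and adequacy of prenatal care (2 months only in the section 8.0 table), use treatment and fixed site only.
4. For each between-arm comparison, report the site- and baseline-adjusted OR or mean difference (site-adjusted only under item 3) with its 95% interval, alongside the unadjusted tests.

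The cost is wording. Site is recorded for stratification, and section 3.2 already schedules the baseline assessment. State the downside: the adjusted OR is conditional on site (and baseline). For site alone its interval factor rises from about 2.03 to 2.06 at 40/60 and 2.17 at 30/70, still within the 2 to 3 of section 10.2.2.
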